The aim of this study is to explore the efficacy of a single intra-operative dose of methadone in patients with idiopathic scoliosis undergoing multi-level posterior instrumentation and spinal fusion. The primary endpoints is the total opioid usage during POD (postoperative day) 0-4. Secondary endpoints include and pain scores during rest and with activity (getting out bed and ambulation) on POD 0-5 and side effects of pain medications

Section E: Protocol Risks/Subjects

E1. Risk Category

Category 2: Research involving greater than minimal risk, but presenting the prospect of direct benefit to the individual subjects.

E2. Subjects

Gender:
Both

Age:

Adolescent (13-17 yrs), Child (3-12 yrs)

Ethnicity:

All Ethnicities

Primary Language:

English, Spanish

Groups to be recruited will include:

Patients

Which if any of the following vulnerable populations will be recruited as subjects?

Children

Vulnerable populations require special protections. How will you obtain informed consent, protect subject confidentiality, and prevent undue coercion?

Patients presenting for spinal surgery will be identified from the Texas Children's Hospital operating room schedule that is routinely available to pediatric anesthesiologists. This will be cross referenced with the pediatric orthopedic surgeons' operative schedule as these cases are scheduled weeks to months in advance. The chart is reviewed to insure that the patient qualifies based on the inclusion and exclusion criteria.

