This patient and observer blinded prospective randomized study will be performed on patients (aged 10 - 17years, both males and females, from all ethnic backgrounds) undergoing multilevel thoraco-lumbar spine surgery with instrumentation and fusion at Texas Children's Hospital, Houston, TX. After obtaining IRB (Institutional Review Board) approval and written informed consent from each patient or his or her legal representative, 56 patients scheduled for multilevel thoraco-lumbar spine surgery with instrumentation and fusion will randomly be assigned into two groups (control or treatment group) based on a computer generated random number using Random Allocation Software For Parallel Group Randomized Trials. There is an equal chance of being assigned to either group. The control group will be given placebo; whereas the treatment group will receive methadone 0.2 mg/kg intravenously.

Inclusion Criteria:

- 1) Patient age 10 \geq 17 years
- 2) Patients undergoing multilevel thoraco-lumbar spine surgery with instrumentation and fusion

Exclusion Criteria:

- 1) Preoperative methadone therapy
- 2) Inability to use the PCA
- 3) Allergy to methadone or morphine
- 4) Morbid obesity with a body mass index >36.0 kg/m²
- 5) Patients with chronic renal failure defined by serum creatinine >2.0 mg/dL
- 6) Liver failure defined as a history of cirrhosis or fulminant hepatic failure
- 7) Preoperative congenital heart disease or arrhythmias
- 8) Patient refusal to participate in study
- 9) Pregnancy (It is standard of care for all post menarche female patients to undergo a urine pregnancy test prior to surgery).

F2. Procedure

The perioperative management of patients will be in keeping with the current standard practices at Texas Children's Hospital. Before surgery, patients will be asked to rate their baseline pain using a verbal rating scale from 1 to 10 by a member of the research team. In addition, information on preoperative opioid consumption during the last 30 days will be collected.

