Postoperatively, patients will be asked to rate their pain using a validated pain scale (a verbal rating scale where 0 = no pain and 10 = worse pain ever) by a blinded research staff member. These pain scores will be collected at 1 hour after entry into recovery and every 4 hours during the first five days of hospitalization both at rest and during activity by the nurses. The cumulative intravenous opioid requirement at 24, 48, and 72 hour will be recorded. The cumulative breakthrough intravenous opioid requirement after initiation of oral pain medication will also be collected. The level of sedation will be determined using the University of Michigan Sedation Scale. In addition, complications such as the incidence of hypotension (defined as mean arterial blood pressure less than 50 mm Hg), the need for vasopressors, the incidence of respiratory depression (defined as a respiratory rate less than 8 breaths per minute, respiratory arrest, or the need for naloxone), the incidence of hypoxemia or desaturation (defined as oxygen saturation [Sao₂] less than 90% or the need for a supplemental oxygen to maintain Sao₂ greater than 94%), the incidence of cardiac arrhythmias, and the incidence of nausea and vomiting including the treatment of side effects will be also recorded. Upon discharge from the hospital, the patients will be asked to keep a diary consisting of daily opioid usage, episodes of nausea and vomiting, daily activity level, and satisfaction scores. As part of standard routine post-surgical followup in the orthopedic clinic, information is collected from the patients which consist of questionnaires regarding pain scores, functional status, activity level, and quality of life. The research team will collect this information at 3 months and 6 months postoperatively.

Section G: Sample Size/Data Analysis**G1. Sample Size**

How many subjects (or specimens, or charts) will be used in this study?

Local: 98

Worldwide: 98

Please indicate why you chose the sample size proposed:

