The sample size was based on the assumption that opioid use in the first 3 days in the placebo group would be similar to that in a previously published study of the same patient population undergoing spine surgery (mean 275 mg SD 75 mg). A group size of 28 would be required for an 80% power of detecting a 30% reduction in opioid use from 275 to 200 mg at the 0.05 level of significance. Allowing for a 50% dropout rate for incomplete data, we will recruit 49 patients in each group for a total of 98 subjects.

G2. Data Analysis

Provide a description of your plan for data analysis. State the types of comparisons you plan (e.g. comparison of means, comparison of proportions, regressions, analysis of variance). Which is the PRIMARY comparison/analysis? How will the analyses proposed relate to the primary purposes of your study?

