The primary endpoint of the study is the morphine consumption during the first 72 postoperative hours. The secondary outcomes include pain scores and the incidence of side effects such as respiratory depression, nausea, and vomiting. Continuous data including pain scores will be first examined for a normal distribution by the Shapiro χ Wilk test. The outcome variables between the two groups will be compared with Student's t -test where appropriate, for normally distributed continuous data or by nonparametric tests if the data were not normally distributed. It is anticipated that the distribution of pain scores will not be normal and that non-parametric tests will be required. Categorical data including patient gender, ASA physical status, incidence of side effects (respiratory depression, need for oxygen beyond the first 2 hours, nausea and vomiting) will be compared by Fisher's exact test. Analysis of variance for repeated measures will be performed to compare differences in pain scores between the treatment groups with time. Data will be presented as mean, standard deviation, median values or numbers (percentages). P values less than 0.05 will be considered statistically significant. In order to maintain a robust statistical analysis, we will also examine the differences in subjects with and without completely evaluable data in known factors that affect postoperative pain after spine surgery (e.g., age, gender, ASA physical status, duration of surgery, intraoperative opioids medications, time of the PACU stay, mean and peak pain scores and recorded opioid consumption in the PACU before discharge). Failure to show a difference in these factors may suggest that the missing data can be considered to be missing at random.

Section H: Potential Risks/Discomforts

H1. Potential Risks/Discomforts

Describe and assess any potential risks/discomforts; (physical, psychological, social, legal, or other) and assess the likelihood and seriousness of such risks:

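### The only missing-data step in G2 draws a wrong inference: finding no difference between complete and incomplete cases cannot support missing at random

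*Combined protocol and SAP*

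**What the plan says.** G1 raises the group size from 28 to 49, with this reason: "Allowing for a 50% dropout rate for incomplete data". It does not say which data are expected to be incomplete.

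G2 lists the tests: Student's t-test or a nonparametric test, Fisher's exact test, and repeated-measures analysis of variance for pain scores. It names no analysis set and gives no rule for a patient whose primary total is incomplete. Its one step on missing data is that "we will also examine the differences in subjects with and without completely evaluable data", on factors such as age, gender, ASA status, duration of surgery and PACU pain and opioid use. It then concludes: "Failure to show a difference in these factors may suggest that the missing data can be considered to be missing at random".

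The primary quantity itself is given in two ways. In G2: "The primary endpoint of the study is the morphine consumption during the first 72 postoperative hours". In Section D: "The primary endpoints is the total opioid usage during POD (postoperative day) 0-4".

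On data capture, F2 states: "The cumulative intravenous opioid requirement at 24, 48, and 72 hour will be recorded". After discharge, "the patients will be asked to keep a diary consisting of daily opioid usage".

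**The concern.** The last sentence of G2 reads a non-significant comparison as support for missing at random. That is the wrong target. Under missing at random, the chance that a total is missing may depend on observed factors, so complete and incomplete cases may differ on them. What it excludes is further dependence on the unseen total once the observed data are taken into account, and a comparison of observed factors cannot test that.

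The sentence matters because nothing else in the plan deals with missing primary data. If the primary test were run on complete cases, a passed check would be offered as the reason to trust it. Yet the condition that biases the treatment comparison, namely loss related to opioid use differently in the two arms, is one that the check does not examine.

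**Working it through.** **1. The allowance in G1.** Inputs are 28 evaluable and 49 recruited per group, with 50% stated.
- Loss implied by 28 and 49: 1 - 28/49 = 43%.
- Complete cases left if half of 49 are lost: 49 x 0.5 = 24.5. Keeping 24 is a loss of 25/49 = 51%.

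So 43-51% is the range the plan allows for, if the allowance applied in full to the primary total.

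**2. Is power the problem?** The planned difference is 275 - 200 = 75 mg with SD 75, a standardised difference of 1.0. A two-sided 5% t-test (G1 does not state sidedness) has 92% power at 24 per group and 96% at 28. Power is not the concern.

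**3. What the check can detect.** If half of the 98 patients are incomplete, the comparison is 49 v 49. At 43% loss it is 56 v 42. The SD differences below are my assumptions; the plan gives none.

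| True difference on a factor | Power, 49 v 49 | Power, 56 v 42 |
|---|---|---|
| 0.3 SD | 31% | 31% |
| 0.4 SD | 50% | 49% |

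A moderate difference on any one continuous factor would therefore be missed at least half the time. Because the comparison is not described by arm, opposite patterns in the two arms could also cancel.

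**4. What complete-case analysis could do.** This is an illustration with assumed inputs: 49 per arm, SD 75, no true effect, and a correlation rho between the tendency to be lost and the opioid total. If a fraction p of an arm is kept, the kept mean shifts by about rho x SD x phi(z)/p, where z is the standard normal quantile of p and phi is the normal density. With rho = 0.3 in one arm and 0 in the other:
- 24 kept, p = 0.490: 0.3 x 75 x 0.399/0.490 = 18.3 mg
- 28 kept, p = 0.571: 0.3 x 75 x 0.393/0.571 = 15.5 mg
- 37 kept, p = 0.755: 0.3 x 75 x 0.314/0.755 = 9.4 mg
- 44 kept, p = 0.898: 0.3 x 75 x 0.178/0.898 = 4.5 mg

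Simulation of the t-test agrees and adds the false-positive rate:

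| Kept per arm (loss) | Bias | False positives |
|---|---|---|
| 24 (51%) | 18 mg | 13% |
| 28 (43%) | 15 mg | 12% |
| 37 (24%) | 9 mg | 8% |
| 44 (10%) | 4 mg | 6% |

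At 24 or 28 kept, dependence of 0.3 in one arm and 0.2 in the other gives 5-6 mg and 6%. Equal dependence of 0.3 gives about 0 mg and 5%.

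**5. What the recorded opioid amounts can recover.** Multiple imputation within arm was simulated at 24 kept, one-arm dependence 0.3 on the unseen total. Assumed correlations with the 72 h total were 0.8 for 48 h opioid, 0.6 for 24 h, 0.3 for PACU opioid, and 0.2 for age and for duration of surgery.

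| Analysis | Bias remaining |
|---|---|
| Complete cases | 18 mg |
| Imputed from 48 h, 24 h and PACU opioid | 6 mg |
| Imputed from 24 h and PACU opioid | 11 mg |
| Imputed from PACU opioid, age and duration | 15 mg |

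With loss unrelated to opioid use and a true difference of 75 mg, power goes from about 92% (complete cases) to 98% when 48 h opioid is observed. It goes from about 93% to 88% when only PACU opioid, age and duration are available.

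**The case against.** The strongest reply is that the 72 h total is an inpatient quantity. F2 keeps the PCA available through the POD 3 transition and records cumulative intravenous opioid at three fixed times. The items more exposed to loss are the 4-hourly pain scores, the diary and the 3- and 6-month questionnaires. This stands. A reader might infer from G1 that about half of the primary totals will be missing; the documents do not say so, and at 10% loss the illustrated harm is small. It does not settle the matter, because G1 attaches the allowance to the sample size for opioid use, and the Section D window runs beyond 72 h.

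A second reply is that F1 describes "This patient and observer blinded prospective randomized study" with a single intraoperative infusion, so loss tied to opioid use in one arm only is unlikely. This also largely stands. Blinding makes one-sided loss less likely without excluding it, since side effects, for example, could differ by arm.

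A third reply is that the sentence is hedged and that no planned analysis depends on the check. The hedge softens the claim but still points it at the wrong question. As the only missing-data text, it is what a report would lean on.

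**Conclusion.** The inference in G2 is wrong in principle, whatever the amount of missing data, and the plan leaves the analysis set and the handling of an incomplete primary total unstated. That much rests on the text alone.

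The size of any harm does not. A reader might go further and infer that the primary result will be biased, or that the plan commits to complete cases. The documents support neither. Complete-case analysis is the natural reading but is not stated, and bias requires loss related to opioid use differently by arm. Under the assumed one-arm dependence of 0.3, the bias runs from about 4 mg at 10% loss to 18 mg at 51% loss, or 5% to 24% of the planned 75 mg effect (4/75 and 18/75). It can go in either direction. Equal dependence gives essentially none. The plan should be corrected before the data are analysed. The point is not a forecast that the trial will mislead.

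**What to change.** - Delete the missing-at-random sentence. Keep the comparison of complete and incomplete cases as description, reported by arm.
- Reconcile Section D with G2 so that one primary endpoint and window is stated; until then it is not defined which totals are missing.
- State that the primary analysis includes all randomised patients in their assigned arm and uses every opioid amount recorded in that window.
- Report the number of missing primary totals, and the reasons, by arm.
- Where a total is missing but 24 h or 48 h opioid is recorded, use those values through multiple imputation within arm or a likelihood-based repeated-measures model. Show the complete-case result alongside.
- Add a sensitivity analysis that shifts the imputed methadone-arm values. The step size and the predictor set are for the sponsor's statistician to choose.

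The cost is SAP wording, modest extra analysis, one added field (reason for missing) and reliance on an imputation model. F2 already plans to record the 24 h and 48 h amounts, and G2 refers to recorded PACU opioid. The gain is not guaranteed: without 24 h or 48 h opioid, imputation loses some power and leaves most of the bias. The plan should therefore also report how many patients with a missing total have 48 h data.

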In this study, we are comparing the addition of another opioid pain medication to reduce pain scores and overall total hospital opioid consumption. Current standard practices for patients undergoing multi-level spine surgery will be used with the exception of methadone given to the treatment group. Methadone may induce prolongation of the rate-corrected QT interval (QTc); however, patients with cardiac arrhythmias or congenital heart disease will be excluded from the study. Side effects of respiratory depression from methadone should not be greater than with typical morphine usage.

Additional risks of the study are the small chance of loss of privacy. The data will be coded. No data identifying the patient will be extracted from the medical records and all data will be kept locked in the offices of the Principal Investigator. Any electronic version will be kept in a password protected network servers controlled by the IT services at the TCH. Computers with access to this network are kept in a locked office where entry is limited to those with an ID key card. This office is located inside the office of the Department of Anesthesiology at Texas Children's Hospital. Unauthorized individuals would not be able to enter these facilities. The likelihood of such events is minimal.

H2. Data and safety monitoring plan

Do the study activities impart greater than minimal risk to subjects?

Yes

NOTE: The answer to the questions in H2 requires the completion of the form: 'Section H – Data and Safety Monitoring Plan' as an attachment in Section S.

H3. Coordination of information among sites for multi-site research

Is the BCM Principal Investigator acting as the SPONSOR-INVESTIGATOR for this multi-site research?

No or Not Applicable

Is BCM the COORDINATING CENTER for this multi-site research?

No or Not Applicable

Section I: Potential Benefits

Describe potential benefit(s) to be gained by the individual subject as a result of participating in the planned work.

Patients assigned to the methadone group may have reduced postoperative pain scores and a reduction of total consumption of postoperative opioids. Patients with less opioid use may benefit from fewer side effects. However, it is possible that there will be no benefits from participating in the study.

Describe potential benefit(s) to society of the planned work.

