Data from this study can be used to determine if methadone provides better pain control in the perioperative setting. Knowledge obtained from this study may allow anesthesiologists from other institutions caring for children and adolescents undergoing similar painful procedures to use this medication to reduce pain.

Do anticipated benefits outweigh potential risks? Discuss the risk-to-benefit ratio.

The risks in this study do not vary from the risks of standard practices at TCH for children undergoing multi-level thoracolumbar spinal instrumentation and fusion. The additional minor risk of an unlikely loss of privacy is outweighed by the societal benefits from this knowledge.

Section J: Consent Procedures

J1. Waiver of Consent

Will any portion of this research require a waiver of consent and authorization?

No

J1a. Waiver of requirement for written documentation of Consent

Will this research require a waiver of the requirement for written documentation of informed consent?

No

J2. Consent Procedures

Who will recruit subjects for this study?

PI
PI's staff

Describe how research population will be identified, recruitment procedures, any waiting period between informing the prospective participant and obtaining consent, steps taken to minimize the possibility of coercion or undue influence and consent procedures in detail.

Patients presenting for spinal surgery will be identified from the Texas Children's Hospital operating room schedule that is routinely available to pediatric anesthesiologists. This will be cross referenced with the pediatric orthopedic surgeons' operative schedule as these cases are scheduled weeks to months in advance. The chart is reviewed to insure that the patient qualifies based on the inclusion and exclusion criteria. The study staff will ask the surgeon if they may approach the patient and parents about the study.

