Potential subjects will be approached about participation on their visit to our preoperative screening clinic which occurs a few days prior to surgery. The child will be approached with parental presence during the preoperative screening visit and age appropriate language will be used to explain the study and answer any questions. Every opportunity will be given to answering questions and discussing their options throughout the study. Enrollment in the study will only occur if the child assents and the parent consent. Voluntary participation will be emphasized during recruitment of patients. A copy of the IRB approved written consent form will be given to parents with time allowed for reading and considering enrollment. Another opportunity to raise questions will be presented on the day of surgery in the holding area. All questions will be fully answered and the child will then be asked to sign their name on the assent portion with parent signing consent. A copy of the signed consent form will be given to parents.

A TCH translator or a Spanish-speaking research staff will thoroughly explain the study to the child and the parent. After all questions are answered and the study staff is assured that the study is understood and participation is agreed, the child will sign their name on the assent portion parent signing consent. A copy of the consent will be given to the parent.

Are foreign language consent forms required for this protocol?

Yes

Which of the following ways will you document informed consent in languages other than English?

A full-length informed consent document

J3. Privacy and Intrusiveness

Will the research involve observation or intrusion in situations where the subjects would normally have an expectation of privacy?

Yes

J4. Children

Will children be enrolled in the research?

Yes

J5. Neonates

Will non-viable neonates or neonates of uncertain viability be involved in research?

No

J6. Consent Capacity - Adults who lack capacity

Will Adult subjects who lack the capacity to give informed consent be enrolled in the research?

No

J7. Prisoners

Will Prisoners be enrolled in the research?

No

Section K: Research Related Health Information and Confidentiality

Will research data include identifiable subject information?

Yes

Information from health records such as diagnoses, progress notes, medications, lab or radiology findings, etc.

Yes

Specific information concerning alcohol abuse:

No

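### Exclusion 7, the only stated safeguard against methadone's QTc risk, does not cover QT-prolonging medication or a charted long QTc, and covers known long-QT syndrome only by interpretation

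*Combined protocol and SAP*

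**What the plan says.** Section H1 of the combined protocol and SAP states the risk and the response together: "Methadone may induce prolongation of the rate-corrected QT interval (QTc); however, patients with cardiac arrhythmias or congenital heart disease will be excluded". The response refers to exclusion 7 in Section F1, which reads in full "Preoperative congenital heart disease or arrhythmias".

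On medication, the only F1 exclusion based on what the child is already taking is exclusion 1, "Preoperative methadone therapy". The only preoperative medication history that Section F2 asks for is opioid use: "information on preoperative opioid consumption during the last 30 days will be collected".

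Eligibility is checked from the record. Sections E2 and J2 both say: "The chart is reviewed to insure that the patient qualifies based on the inclusion and exclusion criteria". Section K answers yes to using "Information from health records such as diagnoses, progress notes, medications, lab or radiology findings, etc".

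After dosing, the complications recorded under F2 include "the incidence of cardiac arrhythmias, and the incidence of nausea and vomiting". Section H2 classes the study as greater than minimal risk and points to a separate Data and Safety Monitoring Plan attached in Section S. That attachment is not among the documents reviewed.

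**The concern.** The risk named in H1 is a drug effect on the QT interval. The safeguard offered is a criterion about structural heart disease and rhythm diagnoses. The two overlap only in part. A child can have a long QTc on an earlier ECG without an arrhythmia diagnosis, and a child with no cardiac diagnosis can be taking another drug that prolongs the QT interval.

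At stake is who may be randomised to a single 0.2 mg/kg intravenous dose of methadone. The participants are aged 10 to 17. If the criterion is applied as written, a child whose chart already holds a reason for caution with a QT-prolonging drug can pass screening. The information needed to stop this is in the record that staff already open, but nothing in F1 tells them to act on it.

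**Working it through.** No figure in the plan bears on this point, so the check is of the text: take each kind of child at known QT risk and ask which of the nine F1 exclusions would stop enrolment.

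**Step 1. What each exclusion covers.** Exclusions 2 to 6, 8 and 9 concern PCA use, allergy to methadone or morphine, body mass index, renal failure, liver failure, refusal and pregnancy. None concerns the QT interval. That leaves exclusion 1 (methadone before surgery) and exclusion 7 (congenital heart disease or arrhythmias).

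**Step 2. Apply those two to each group.**

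| Child | Exclusion 1 | Exclusion 7 | Result under F1 as written |
|---|---|---|---|
| Known long-QT syndrome | Does not apply | Applies if the screener counts it as an arrhythmia | Depends on interpretation |
| Prolonged QTc on an ECG in the chart, no arrhythmia diagnosis | Does not apply | Not named | Eligible |
| Regular QT-prolonging medication other than methadone, no cardiac diagnosis | Does not apply | Does not apply | Eligible |

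**Step 3. Look for the safeguard elsewhere.** In the supplied text the QT interval is mentioned only in H1, and no ECG is mentioned anywhere. F2's medication history is limited to opioids over 30 days, so it would not bring other QT-prolonging drugs to light. F2's recording of arrhythmias happens after dosing and cannot affect eligibility.

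**Step 4. Is the information available before randomisation?** Yes. E2 and J2 describe a chart review against the criteria, for cases scheduled weeks to months ahead, and the family is approached at a clinic visit a few days before surgery. Section K puts diagnoses and medications from the health record within the research data. The second and third groups could be found at that review if F1 named them.

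**Step 5. Can the size be computed?** The expected number of such children in the methadone arm would be n × p. Here n is 28 (half of the 56 in F1) or 49 (per group in G1), and p is the proportion of otherwise eligible children affected. The documents give no value or range for p, and they give no rate of harm after a single dose. The calculation stops there.

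**The case against.** The strongest case against has four parts.

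- **Long-QT syndrome is arguably covered already.** A clinician may well treat it as an arrhythmia under exclusion 7. This stands: for that group the change only clarifies the wording. It does not reach a charted QTc value without a diagnosis, or medication.
- **Part of the safety plan is unseen.** The Section S attachment may require ECG or rhythm monitoring, and J2 has staff ask the surgeon before approaching the family. Either could lower the residual risk, which limits how serious the point can be. Monitoring after enrolment does not alter F1, and the request to the surgeon is not described as a QT check.
- **The remedy needs more than a few added words.** A QTc limit and a drug list must be set or staff will apply the criterion unevenly, and the QTc clause reaches only children who happen to have an earlier tracing. Both remarks are fair.
- **No harm is quantified.** True. A reader might pick a rate for p and turn it into a chance that at least one such child is dosed. That percentage would only restate the assumed rate, would pool a diagnosis with medication use, and would measure exposure rather than harm.

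A reader might also infer that the plan will leave arrhythmias unanalysed, because the G2 comparison names "incidence of side effects (respiratory depression, need for oxygen beyond the first 2 hours, nausea and vomiting) will be compared" and not arrhythmia. The text does not support that. G2 introduces its categorical data with *including* and its side effects with *such as*, so both lists are open. Hypotension, vasopressor need and sedation are likewise recorded under F2 and unnamed in that bracket. Naming arrhythmia would add little as a test: against 0 events on placebo, Fisher's exact test needs 6 on methadone for p<0.05 (p=0.023 with 28 per arm, 0.027 with 49), since 5 gives 0.052 and 0.056.

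**Conclusion.** The point holds as an inexpensive safety improvement of minor to moderate weight. In the supplied text, exclusion 7 is the only stated answer to a risk the protocol itself names. It leaves two identifiable groups eligible: children on regular QT-prolonging medication, and children with a prolonged QTc in the chart but no arrhythmia diagnosis. Known long-QT syndrome is covered only by interpretation. The gap for medication is the clearest, because no reading of F1 covers it.

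This rests on the wording of F1, F2 and H1 and on no assumed rate. It does not show that any such child will present, or that a single dose would harm one. Nor does it show that the trial lacks cardiac monitoring: a reader might infer that from the absence of any ECG, but the Section S plan has not been seen.

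**What to change.** Extend exclusion 7 in F1 to read: congenital heart disease; arrhythmias; known long-QT syndrome; a prolonged QTc on any ECG already in the chart (limit set in advance with cardiology); or current regular QT-prolonging medication (from a pre-specified drug list). Check all of these at the existing chart review, before enrolment.

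The cost is one amended criterion, one QTc limit and one drug list. No new ECG, visit or endpoint is needed. Some otherwise eligible children will be excluded. This should be few, but the documents do not allow a count. Because the exclusion is applied before randomisation, it does not bias the comparison between arms.
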